### 6.3.6.2 Secondary Analysis

The secondary efficacy endpoints are described in Section 3.2. All secondary efficacy endpoints defined in this section will be analysed as exploratory.

For categorical variables, a summary of these endpoints will be presented at each specified timepoint by treatment group and will include the number and percentage of each category with the 95% CI. A chi-square test or Fisher Exact test, as appropriate will be performed to compare proportions between treatments at each timepoint.

For continuous variables: VAS photophobia, Snellen best-corrected visual acuity (BCVA) score and VAS pain score, a summary of these endpoints will be presented at each specified timepoint by treatment group. Change from baseline will be derived and presented in the same way.

For variables: Anterior chamber cell grades, anterior chamber flare grades, severity of signs of ocular inflammation and eye discomfort grades categorical and continuous summary statistics will be presented, changes from baseline will also be derived and will be presented as increase, decrease or not change table. In the same way, a table with 2 categories: Improvement and no improvement (increase+no change) will be presented. A chi-square test or Fisher Exact test will be performed to compare proportions between treatments:

Change from baseline to Day 3		
Anterior Chamber Cell Grade	IMP	Placebo
Decrease (Improvement)	n (%)	n (%)
No change	n (%)	n (%)
Increase (Worsening)	n (%)	n (%)
P value chi-square or Fisher	p-value	
Improvement	n (%)	n (%)
No Improvement	n (%)	n (%)
	p-value	

No Improvement = increase + no change

For the variables mentioned above, to see the proportion of patients with different grades, a descriptive table like the following will also be built, no statistical inference will be made:

Grade	IMP			Placebo		
	Baseline	Day X	Change	Baseline	Day X	Change
0	n (%)	n (%)	(%)	n (%)	n (%)	(%)
0.5+	n (%)	n (%)	(%)	n (%)	n (%)	(%)
1+	n (%)	n (%)	(%)	n (%)	n (%)	(%)
2+	n (%)	n (%)	(%)	n (%)	n (%)	(%)
3+	n (%)	n (%)	(%)	n (%)	n (%)	(%)
4+	n (%)	n (%)	(%)	n (%)	n (%)	(%)

Between treatment comparison of the evolution over time will be analysed using a Restricted Maximum Likelihood (REML)-based repeated measures approach (Mixed Model Repeated Measures [MMRM]). The model for analysis will include the change from baseline as a dependent variable, the baseline score as a covariate, the categorical fixed effects of treatment (IMP, Placebo) and visit and the interaction treatment\*visit. An unstructured (co)variance structure will be used to model the within-patient errors. If this analysis fails to converge, alternative covariance structures will be tested. Akaike's information criterion will be used to determine the best fit (smaller AIC).

If it is not possible to apply a MMRM due to the non-normality of the variable, the Mann Whitney Wilcoxon test will be performed.

Secondary efficacy analyses will be performed on the FAS population.

The PP population set will be also tested to confirm the robustness of the secondary analyses.

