## 5. STUDY POPULATION

### 5.1 Inclusion Criteria

Patients will be eligible for study participation if they meet all of the following criteria:

- 1) Male or female, age 18 years or older on day of consent
- 2) Patients with routine unilateral cataract surgery on the day prior to study randomization
- 3) Patients with at least 5 cells in anterior chamber on the first day after surgery (at Visit 1)
- 4) Willing and able to understand and provide written ICF (at Visit -1)
- 5) Women who satisfy one of the following:
  - a) Are of child-bearing potential who are not pregnant or lactating and who are either abstinent or sexually active on an acceptable method of birth control (methods that can achieve a failure rate of less than 1% per year when used consistently and correctly, like hormonal contraception (oral pills, implantable device, or skin patch), intrauterine device, bilateral tubal occlusion, or double barrier) for at least 4 weeks prior to Visit 1 and throughout the study (i.e., until Day 29),  
OR
  - b) Are post-menopausal (have had no menstrual cycle for at least one year prior to Visit -1) or have undergone a sterilization procedure (bilateral tubal ligation, hysterectomy, hysterectomy with unilateral or bilateral oophorectomy or bilateral oophorectomy) at least 6 months prior to Visit -1

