## 9. STATISTICAL METHODS

### 9.1 General Statistical Methods

In general, data will be summarized by means of summary statistics. Continuous data will be presented with the number of observations, mean value, confidence intervals, standard deviation, minimum, Q1, median, Q3 and maximum value. Change from baseline to each post-baseline visit will be also described using descriptive statistics. Categorical data will be presented as counts and percentages.

The data will be presented for each treatment group by visit.

Individual patient data will be listed for all enrolled patients. Listings will be sorted by center and patient number and labelled by randomized treatment group.

Before unmasking the study data, a separate statistical analysis plan (SAP), which will provide the technical details of the statistical analysis outlined below, will be prepared and approved.

For statistical analyses, the following definitions will be applied:

- Baseline: Baseline is defined as Visit 1 (Day 1, 24 h after the cataract surgery).
- Randomized treatment group: The treatment that was assigned at the time of randomization.

The assessments performed at Visit 1 (Day 1) will be considered the baseline values.

All data collected during study follow-up will be displayed and analyzed according to the actual visit data in the eCRF.

Unless otherwise stated, all statistical tests will be conducted using two-sided alpha = 0.05.

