#### 9.1.1 *Sample Size*

A two group  $\chi^2$  test with a 0.05 two-sided significance level will have 80% power to detect the difference between a proportion with complete resolution of anterior chamber cells in the active group of 0.22 and the placebo group proportion of 0.07 (odds ratio of 3.747) when the sample size is 202. Considering a 4% lost to follow-up rate a final sample size of 210 patients will be required (140 clobetasol, 70 placebo, in a 2:1 randomization ratio).

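### The two-level Improvement test counts patients without the sign at baseline as not improved, and the ordered change is tested without order or baseline grade; this costs sensitivity in exploratory tables

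*SAP*

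**What the plan says.** SAP 6.3.6.2 takes cell grade, flare grade, severity of the ocular signs and discomfort grade and derives the direction of change from baseline at each visit. Two tables follow. One has three levels (decrease, no change, increase). The other has two: improvement, and "no improvement (increase+no change". For both, "A chi-square test or Fisher Exact test will be performed to compare proportions between treatments". Neither denominator is limited to patients who had the sign at baseline, and no stratified, adjusted or ordinal test is named. The full grade-by-visit table is descriptive only.

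SAP 6.3.1 defines grade 0 of a sign as its absence. SAP 6.5 uses baseline as a covariate only in the MMRM of continuous endpoints. The MMRM tables listed in SAP 8.1 cover photophobia, BCVA, VAS pain and diary pain, so none covers the graded signs or discomfort. SAP 6.3.6.2 labels all these endpoints exploratory.

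Cell grade differs from the others. Protocol 5.1 admits "Patients with at least 5 cells in anterior chamber on the first day after surgery", and SAP Table 1 puts 1-5 cells at grade 0.5+ and 6-15 at 1+. No eligible patient starts at cell grade 0.

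**The concern.** A patient with no flare at baseline and none at Day 8 has the best possible course. The derivation calls this no change, and the two-level table pools it with worsening. The improvement rate therefore cannot exceed the baseline prevalence of the sign, and rates cannot be compared across signs of different prevalence.

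This applies to seven two-level tables, each at four visits: flare (14.2.5.1), chemosis, bulbar conjunctival injection, ciliary injection, corneal edema and keratic precipitates (14.2.11.1, .3, .5, .7 and .9), and discomfort (14.2.16.1).

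A second loss comes from the test. Decrease, no change and increase are ordered, but the Pearson chi-square treats them as unordered and makes no use of how severe the sign was at entry. At stake is the chance of seeing a real effect on these signs, and how readable the tables are.

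**Working it through.** **The plan's own figure.** Protocol 9.1.1 gives power only for the primary endpoint: 0.22 vs 0.07, two-sided 0.05, 2:1, 202 evaluable. The power formula used below is Φ[(|d| − 1.96·SE0)/SE1], with SE0 pooled and SE1 unpooled. At N = 202 it gives (0.15 − 1.96 × 0.0561)/0.0473 = 0.85, that is 80.2%. The odds ratio (0.22/0.78)/(0.07/0.93) = 3.747 is exact, and 202/0.96 = 210.4. The stated size reproduces. The documents give no power for the grade-change tests.

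**Inputs.** From the documents: 140/70 patients and two-sided 0.05. Assumed, because the documents give no baseline grade distribution or effect for these signs:
- Share f with the sign at baseline: 20%, 40% or 60%; their grades 1/2/3 split 60/30/10.
- Resolve / improve one grade / no change / worsen: 65/15/15/5% active and 40/15/30/15% placebo, so 80% vs 55% improve.
- New signs in patients without the sign at baseline: 5% active, 10% placebo.

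**Dilution.** Over all patients the improvement rates are 0.80f and 0.55f, so the difference is 25 × f points:
- f = 20%: 16% vs 11%, 5 points.
- f = 40%: 32% vs 22%, 10 points.
- f = 60%: 48% vs 33%, 15 points.

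For f = 40%: pooled rate (140 × 0.32 + 70 × 0.22)/210 = 0.287, SE0 = 0.0662, SE1 = 0.0633, and (0.10 − 0.1297)/0.0633 = −0.47, so power is 32%. Among the 56/28 patients with the sign, 80% vs 55% gives SE0 = 0.1043, SE1 = 0.1082, and (0.25 − 0.2044)/0.1082 = 0.42, or 66%.

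**Presence/absence by visit (also planned).** A grade-1 patient who improves one step reaches 0, so 65 + 0.6 × 15 = 74% resolve on active and 40 + 0.6 × 15 = 49% on placebo. The sign is then present in f × 26% + (1 − f) × 5% vs f × 51% + (1 − f) × 10%, a difference of 25f + 5(1 − f) points: 9, 13 and 17.

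**Power by simulation at 140/70.** Repeat runs move single figures by up to about 3 points.

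| Test | f = 20% | f = 40% | f = 60% |
|---|---|---|---|
| Planned two-level, all patients | 14% | 31% | 55% |
| Planned three-level chi-square | 33% | 47% | 64% |
| Planned presence/absence | 46% | 64% | 78% |
| Two-level, baseline grade ≥1 only | 40% | 67% | 82% |
| Mean-score test stratified by baseline grade | 53% | 71% | 83% |

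With new signs at 5% in both arms, the stratified test gives 30% at f = 20% and 78% at f = 60%. The presence/absence difference then falls to 25f, or 5, 10 and 15 points.

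**A milder effect** (60% vs 40% improve). The only related figure in the documents is in Protocol 2.1: 55% with no pain or discomfort after surgery, in background literature. Carried over to discomfort, f = 45%: 27% vs 18%, power 29% over all patients and 45% restricted.

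**Order alone.** Assume decrease/no change/increase of 60/35/5 vs 40/45/15, and worsening in 5% vs 15% of patients without the sign. With f = 100% the unordered three-level test has 83% power against 89% for the mean-score test. At f = 70% it is 71% vs 82%, and at f = 45% 66% vs 77%, with the mean-score test stratified by presence of the sign at baseline.

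**Null check.** With equal arms at f = 45%, all the tests reject in about 5% of trials.

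**The case against.** The strongest reply is that the two-level table is only one of several planned views. SAP 8.1 also compares presence or absence of each sign by visit (14.2.9.1 to 14.2.9.5), absence of discomfort (14.2.17.1), and cell grade 0 with flare grade 0 (14.2.8). In these a patient without the sign counts favourably. This stands, and it limits the point in three ways:
- A reader might infer that the inflammation and discomfort objectives depend on the Improvement tables. They do not depend on them alone.
- A reader might take 14% against 53% as the price of the plan. That compares the weakest planned test with the proposed one. Against the best planned test the gain is 7, 7 and 5 points (53 − 46, 71 − 64, 83 − 78). The size also depends on the assumed effect on new signs: without it, the stratified test at 20% prevalence (30%) falls below the restricted two-level test (about 40%), and the presence/absence difference shrinks as well.
- A reader might infer that absence of a sign is simply reported as lack of benefit. The SAP shell prints no change and worsening on separate rows, and the descriptive grade table shows how many patients are at grade 0. What is missing is a split of the no-change row into absent at both visits and present but unchanged.

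It is also tempting to extend the point to the endpoint of cell grade 1+ or less, since patients entering with 5-15 cells already meet it. That endpoint describes status at the visit, not change, and is valid in all randomized patients. If 20%, 40% or 60% enter at 1+ or below and stay there, and the rest reach it in 70% vs 50%, the observed difference is 16, 12 or 8 points. Power is 67%, 51% or 35%, against 72%, 59% or 43% if restricted. The gain is modest, and restriction would drop patients who enter low and worsen.

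**Conclusion.** The point holds as a loss of sensitivity and clarity in seven exploratory two-level tables, with a smaller loss in the three-level tests. That a patient at baseline grade 0 cannot improve, and that the difference scales with f, follows from the SAP's definitions and needs no assumption. The power figures do rest on assumptions: 14-55% for the two-level test and 33-64% for the three-level test, against 53-83% for a stratified mean-score test, or 30-78% without an effect on new signs.

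The documents do not support a reading of bias or inflated type I error: baseline is balanced in expectation by randomization, and the null check shows about 5%. Nor do they support extending the no-sign problem to cell grade, because entry requires at least 5 cells. The primary and key secondary analyses are not affected.

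**What to change.** In SAP 6.3.6.2 and the table shells:
1. Compare the visit grade between arms with a Cochran-Mantel-Haenszel mean-score test stratified by baseline grade, or a proportional-odds model adjusted for it. This keeps every patient and uses the order.
2. Report Improvement among patients with baseline grade 1 or more, and give patients without the sign at both visits their own row. Baseline is assessed before the first dose, so the restricted comparison remains a randomized one.
3. Keep the endpoint of cell grade 1+ or less in all randomized patients as planned, and add a supplementary table by baseline cell grade.

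The cost is SAP wording, revised shells and slightly more analysis work; baseline grades are already collected. The restricted table has fewer patients, for example 28/14 at 20% prevalence. Protocol 9.2 calls for a protocol amendment when the primary hypothesis or its methods change, which this does not do. The change should be made before unmasking.

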## **2.2 Rationale for the Study**

Cataract surgery is one of the most common surgical procedures performed worldwide. In fact, in 2017, 3.8 million cataracts procedures were performed in the US.

Despite of surgical advances, pain and inflammation after ophthalmic surgery continues to be a burden on both patients and physicians. The treatment of postoperative pain is essential for hospitalized patients, but it is even more important for patients who are treated on an outpatient basis.

Also, pain after ophthalmic surgery may be considered a sign of a possible complication. Severe pain is assumed to be a sign of postoperative inflammation or infection, making it a concern for both patient and physician. However, a surgery without perioperative complications may also be associated with significant postoperative pain during the early

recovery. Thus, appropriate counseling and pain management should be provided to improve quality of life.

Clobetasol propionate ophthalmic nanoemulsion 0.05% will be administered as a topical ophthalmic nanoemulsion.

Patients are expected to self-administer one drop of either clobetasol propionate ophthalmic nanoemulsion 0.05% or placebo control QID.

Direct instillation is the most efficient method for delivery to the ocular surface and is an accepted and widely used method for topical application to the eye. This study will examine effect and tolerability for 14 days of clobetasol propionate ophthalmic nanoemulsion 0.05% dosed QID.

This study is being conducted to support an application for approval to market clobetasol propionate ophthalmic nanoemulsion 0.05% in the US for the indication of inflammation and pain after ocular surgery. The reference (comparator) product in this study, the vehicle, is expected to provide a lower efficacy rate when compared to clobetasol 5%.

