### **9.1.12 Secondary Analysis**

For continuous variables, a summary of these endpoints will be prepared at each specified timepoint and will include an estimate of the mean change from baseline for each treatment group and of the adjusted treatment difference and 95% confidence interval. The between-

treatment comparison will employ a mixed model of repeated measures (MMRM) with treatment as fixed factor and baseline as a covariate.

For categorical variables, a summary of these endpoints will be prepared at each specified timepoint and will include the number and percentage of each category. A chi-square test will be performed. Confidence intervals on the difference between pairwise comparisons of treatments with the placebo group will be computed. These analyses will not be adjusted for study center.

Secondary efficacy analyses will be performed on the FAS population.

The PP population set will be also tested to confirm the robustness of the secondary analyses.

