#### 3.2 Secondary Efficacy Endpoints

Key secondary efficacy endpoint

- Proportion of patients with VAS pain score of “0” (no eye pain) compared to placebo at Day 8.

Eye pain score will be assessed by the patient before any ocular examination and will be scored by ticking on a continuous scale comprised of a 10 cm horizontal line anchored by two verbal descriptions: “no eye pain” (score of 0) and “worst imaginable eye pain” (score of 10).

- Proportion of patients with anterior chamber cell grade of “0” compared to placebo at Day 3, Day 15 and Day 29.

- Change from Baseline to Day 3, Day 8, Day 15 and Day 29 compared to placebo in the proportion of patients with different anterior chamber cell grades.
- Change from Baseline to Day 3, Day 8, Day 15 and Day 29 compared to placebo in the proportion of patients with different anterior chamber flare grades.
- Proportion of patients with anterior chamber cell grade of “≤0.5+” and flare grade of “0” compared to placebo at Day 3, Day 8, Day 15 and Day 29.
- Proportion of patients with anterior chamber cell grade of “≤1+” compared to placebo at Day 3, Day 8, Day 15 and Day 29.
- Proportion of patients with anterior chamber cell grade of “0” and flare grade of “0” compared to placebo at Day 3, Day 8, Day 15 and Day 29.
- Frequency of different signs of ocular inflammation compared to placebo at Baseline, Day 3, Day 8, Day 15 and Day 29.
- Change from Baseline to Day 3, Day 8, Day 15 and Day 29 compared to placebo in the proportion of patients with different signs of ocular inflammation.
- Change from Baseline to Day 3, Day 8, Day 15 and Day 29 compared to placebo in the severity of signs of ocular inflammation.
- Change from Baseline to Day 3, Day 8, Day 15 and Day 29 compared to placebo in the visual analog scale (VAS) photophobia score.
- Change from Baseline to Day 8, Day 15 and Day 29 compared to placebo in Snellen best-corrected visual acuity (BCVA) score.
- Change from Baseline to Day 3, Day 8, Day 15 and Day 29 compared to placebo in the VAS pain score.
- Proportion of patients with VAS pain of “0” compared to placebo at Day 3, Day 15 and Day 29.
- Change from baseline to Day 3, Day 8, Day 15 and Day 29 compared to placebo in the proportion of patients with different discomfort grades.
- Proportion of patients with no discomfort (“None”) compared to placebo at Day 3, Day 8, Day 15 and Day 29.
- Change over time in the VAS pain score reported in the patients’ diaries compared to placebo.

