### 6.5 Adjustment for Covariates

Baseline value will be used as a covariate in the MMRM analyses for the continuous secondary efficacy endpoints (see Section 6.3.6).

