14.2.10.4	Change from Baseline to Day 3, Day 8, Day 15 and Day 29 compared to placebo in the proportion of patients with corneal edema (yes/no)	FAS	
14.2.10.5	Change from Baseline to Day 3, Day 8, Day 15 and Day 29 compared to placebo in the proportion of patients with keratic precipitates (yes/no)	FAS	
14.2.11.1	Change from Baseline to Day 3, Day 8, Day 15 and Day 29 compared to placebo in the severity of chemosis. Improvement or no Improvement.	FAS	
14.2.11.2	Change from Baseline to Day 3, Day 8, Day 15 and Day 29 compared to placebo in the severity of chemosis. Descriptive table	FAS	
14.2.11.3	Change from Baseline to Day 3, Day 8, Day 15 and Day 29 compared to placebo in the severity of bulbar conjunctival injection. Improvement or no Improvement.	FAS	
14.2.11.4	Change from Baseline to Day 3, Day 8, Day 15 and Day 29 compared to placebo in the severity of bulbar conjunctival injection. Descriptive table	FAS	
14.2.11.5	Change from Baseline to Day 3, Day 8, Day 15 and Day 29 compared to placebo in the severity of ciliary injection. Improvement or no Improvement	FAS	
14.2.11.6	Change from Baseline to Day 3, Day 8, Day 15 and Day 29 compared to placebo in the severity of ciliary injection. Descriptive table	FAS	
14.2.11.7	Change from Baseline to Day 3, Day 8, Day 15 and Day 29 compared to placebo in the severity of corneal edema. Improvement or no Improvement.	FAS	

14.2.11.8	Change from Baseline to Day 3, Day 8, Day 15 and Day 29 compared to placebo in the severity of corneal edema. Descriptive table	FAS	
14.2.11.9	Change from Baseline to Day 3, Day 8, Day 15 and Day 29 compared to placebo in the severity of keratic precipitates. Improvement or no Improvement	FAS	
14.2.11.10	Change from Baseline to Day 3, Day 8, Day 15 and Day 29 compared to placebo in the severity of keratic precipitates. Descriptive table	FAS	
14.2.12	MMRM. Change from Baseline to Day 3, Day 8, Day 15 and Day 29 compared to placebo in the visual analog scale (VAS) photophobia score.	FAS	
14.2.13	MMRM. Change from Baseline to Day 8, Day 15 and Day 29 compared to placebo in Snellen best.corrected visual acuity (BCVA) score.	FAS	
14.2.14	MMRM. Change from Baseline to Day 3, Day 8, Day 15 and Day 29 compared to placebo in the VAS pain score.	FAS	X
14.2.15	Proportion of patients with VAS pain of "0" compared to placebo at Day 3, Day 15 and Day 29.	FAS	X

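### The VAS MMRM has one baseline slope for all visits, which costs precision at Day 3 if pain and photophobia fall toward 0; a baseline-by-visit term would recover it

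*SAP*

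**What the plan says.** - **Fixed effects.** SAP 6.3.6.2 takes change from baseline as the outcome and fits "the baseline score as a covariate, the categorical fixed effects of treatment (IMP, Placebo) and visit", with the treatment-by-visit interaction. The fit is by REML, and "An unstructured (co)variance structure will be used to model the within-patient errors".
- **No baseline-by-visit term elsewhere.** SAP 6.5 says only "Baseline value will be used as a covariate in the MMRM analyses for the continuous secondary efficacy endpoints". Protocol 9.1.12 describes the MMRM with "treatment as fixed factor and baseline as a covariate".
- **Outputs.** SAP 8.1 lists Table 14.2.14, "MMRM. Change from Baseline to Day 3, Day 8, Day 15 and Day 29 compared to placebo in the VAS pain score", and Table 14.2.18, the MMRM of diary pain. Both are flagged top-line. Photophobia (Table 14.2.12) and BCVA (Table 14.2.13) use the same model and are not flagged. Protocol 9.1.12 already promises an adjusted difference with a 95% confidence interval at each timepoint.
- **Status.** SAP 6.3.6.2: "All secondary efficacy endpoints defined in this section will be analysed as exploratory".

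**The concern.** Baseline is measured 24 hours after surgery, and the outcome is the later score minus that baseline. For a patient whose later score is 0, change equals minus baseline. As pain resolves, the regression of change on baseline therefore tends to a slope of -1. At Day 3, while scores still track baseline, the slope is less negative. The plan gives reason to expect such a course: Protocol 2.2 says that uncomplicated surgery "may also be associated with significant postoperative pain during the early" recovery, and the key secondary endpoint is a pain score of 0 at Day 8.

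A model with one slope must compromise, and weighted estimation settles close to the visits with the least residual variance. If variance falls as pain resolves, those are the late visits. The Day 3 contrast is then adjusted with the wrong slope, and baseline variation that could have been removed stays in as noise. What is at stake is the width of the visit-specific intervals, chiefly at Day 3.

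**Working it through.** **The plan's own figure.** The documents state no precision for any MMRM. Their only sample-size figure concerns the primary endpoint (0.22 vs 0.07, N = 202, 80% power). It reproduces (power 80.2%, odds ratio 3.747) and has no bearing on this point.

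**Inputs from the documents.** 140 vs 70 patients; visits at Days 3, 8, 15 and 29; unstructured covariance; the fixed effects above.

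**Assumed inputs (not in the documents).** Baseline SD 20 mm. Correlation of the Day 3/8/15/29 scores with baseline 0.6/0.4/0.25/0.15. Visit SDs: steep 15/10/7/5, mild 16/14/12/10, or constant at 20 mm. Residual between-visit correlation 0 to 0.7, exchangeable or AR(1).

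**Formulas (complete data).**
- Slope of change on baseline at visit t: b_t = rho_t × SD_t / 20 - 1.
- Residual SD: s_t = SD_t × sqrt(1 - rho_t²).
- Common slope, with S the residual covariance matrix: b = (1'S⁻¹b_vec) / (1'S⁻¹1).
- Variance ratio, common slope over visit-specific slopes: [s_t² + (b_t - b)² × 20²] / s_t². Interval width goes with its square root.

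**Worked case: steep fall, residual correlation 0.**
- Slopes: 0.6×15/20 - 1 = -0.55; 0.4×10/20 - 1 = -0.80; then -0.9125 and -0.9625.
- Residual SDs: 12.0, 9.17, 6.78, 4.94.
- Weights 1/s_t² as shares: 8.5%, 14.6%, 26.7%, 50.2%. Common slope: -0.89.
- Day 3: (0.34)² × 400 = 46.3. Ratio (144 + 46.3)/144 = 1.32; square root 1.15.
- Day 8: (0.09)² × 400 = 3.3. Ratio (84 + 3.3)/84 = 1.04; square root 1.02.

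**Ranges over residual correlation 0 to 0.7.**

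| SD pattern | Day 3 variance | Day 3 interval | Day 8 interval |
|---|---|---|---|
| Steep | +32% to +71% | +15% to +31% | +2% to +14% |
| Mild | +17% to +35% | +8% to +16% | 0 to +4% |
| Constant | +1% to +8% | +1% to +4% | 0 to +1% |

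If slopes are equal at all visits, every ratio is 1.00.

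**Day 29.** SAP section 5 restricts FAS efficacy analysis to visits on study drug and free of rescue, while treatment lasts 14 days, so Day 29 may not be in the model. Without it, the steep pattern gives Day 3 variance ratios of 1.20 to 1.48, that is, intervals about 10-21% wider.

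**Simulation check.** In 4,000 simulated trials per scenario (134 vs 68, skewed baseline, VAS bounded at 0 and 100, other assumed parameters), the Day 3 standard error was 12-53% larger under the common slope and the Day 8 standard error 5-23% larger. A control with equal slopes gave 1.00. Mean estimates under the two models differed by at most about 0.02 mm.

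**Chance baseline imbalance (steep, correlation 0).** One standard error of the baseline difference is 20 × sqrt(1/140 + 1/70) = 2.93 mm. It shifts the Day 3 contrast by 0.34 × 2.93 = 1.0 mm, against a fully adjusted standard error of 12 × 0.146 = 1.76 mm. Combined, sqrt(1.76² + 1.0²) = 2.02, and 2.02/1.76 = 1.15: the same 15% as above, not an addition to it.

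**The case against.** **Stakes are low. This stands.** The affected endpoints are exploratory, and the primary and key secondary tests are unadjusted chi-square tests. The unstructured covariance lets the standard error reflect the extra variance.

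**The size rests on assumptions. This stands.** No VAS mean, SD or correlation is given, and the Day 3 loss runs from 1% to 31% of interval width over the ranges used. A reader might infer that the loss is established, or that it is sizeable at both early visits. The documents support neither. At Day 8, the visit that matches the one-week pain objective, the loss is mostly small, and no passage says that a pain effect is expected at Day 3.

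**It might be read as bias.** A reader might infer that the common slope carries baseline imbalance into the early contrasts as a separate fault. Conditional on a given imbalance there is a shift, but it averages out over randomization and is already counted in the variance ratio. These calculations assume complete data; the effect of visits removed for rescue was not quantified.

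**BCVA.** Extending the argument to BCVA is not supported. It has no Day 3 analysis, and nothing forces acuity toward 0.

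**The MMRM may not be used.** SAP 6.3.6.2 substitutes a Mann-Whitney-Wilcoxon test if non-normality rules the model out. Many zero scores are plausible: Protocol 2.1 cites 55% of patients without pain or discomfort after surgery, although not in this trial's selected population. The point applies only where the MMRM is fitted.

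None of this gives a reason to prefer the common slope.

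**Conclusion.** The point holds as a low-priority refinement. The SAP's model imposes one baseline slope, and if VAS pain and photophobia fall toward 0 with falling variance, the Day 3 treatment difference is estimated less precisely than the data allow. With baseline SD 20 mm and the correlations listed, the Day 3 interval is about 15-31% wider (steep), 8-16% wider (mild) or 1-4% wider (constant SD), and there is no loss if slopes are equal. The direction follows from the model once scores converge; the size cannot be fixed from the documents. Nothing here supports a claim of bias on average over randomization, of type I error inflation, or of any effect on the primary or key secondary result.

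**What to change.** - In SAP 6.3.6.2, and correspondingly in 6.5, add the baseline-by-visit interaction to the MMRMs for visit VAS pain and VAS photophobia. This costs 3 degrees of freedom for four visits with about 210 patients, and fewer if Day 29 is excluded. State whether Day 29 is in the model under the section 5 rule.
- Add the corresponding baseline-by-time term to the diary pain MMRM (Table 14.2.18). Its cost depends on how diary time is coded.
- For BCVA (Days 8, 15 and 29; 2 degrees of freedom) the term is optional.
- Keep the visit-specific adjusted differences and 95% confidence intervals already promised in Protocol 9.1.12.

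The cost is negligible rather than strictly zero. No new data are needed, the primary test does not change, and the term can be pre-specified before unmasking.
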